#### 1.5.3 **BASELINE TESTING:**

There are multiple outcome measurement sessions at baseline. There is an 8-week maximum window to complete these measures. The 8-week window starts the day the informed consent is signed at session 1. Any measures or sessions collected outside of this window would not determine eligibility, but would be classified as a protocol deviation. Further, the order of these sessions and measures might be re-ordered based on availability and timing of available slots.

#### **Session 1: ELIGIBILITY AND FITNESS TESTING**

Before the session, participants will receive a reminder phone call and will be instructed to refrain from exercise or drinking alcohol after 9:00 pm the night before, no over-the-counter medications 12 hours prior to the appointment, no smoking, using nicotine, or consuming caffeine 3 hours before the visit. Informed consent will be obtained during the first session (~ 3 hours). Participants will have their blood pressure taken (clinical read) to re-verify eligibility. Measurement of the participants height and weight will be taken using a validated stadiometer. Participants will be asked to bring their medications in a bag for verification. Once the participant is deemed eligible, they will fill out several questionnaires

before undergoing a CRF test. Participants will complete a maximal VO2 test to assess CRF following a Modified Balke Protocol with an agreed upon speed between the participant and lead exercise physiologist. The session will first start by a warm-up session of 5 minutes followed by a blood-pressure reading. Only participants with safe blood pressure readings (>220/110) will be allowed to continue. The participant will walk on a motor-driven treadmill with constant speed and increments of the incline. The intensity is increased in two-minute stages. We will collect all of the exhaled air by having the individual wear a fitted facemask that collects the exhaled air which then travels through a tube to the analyzer. This assessment usually takes about 15 - 30 minutes to complete depending on the starting fitness level of the participant. These procedures are recommended by the American College of Sports Medicine for graded exercise testing. During the exercise test, heart rate is continuously monitored via ECG along with blood pressure readings and Rating of Perceived Exhaustion (RPE) every two minutes. When the participant reaches the endpoint goal of the exercise test (symptom limitation and/or volitional exhaustion), the facemask will be removed and they will undergo a four-minute active cool-down in which they will walk at a slower rate with zero incline grade. After these four minutes the participant will be helped off of the treadmill and will undergo a passive cooldown session in which they are seated in a chair. The participant's heart rate and BP will be continuously monitored through the cool-down period every two minutes and the participant will not be allowed to leave until the vital signs return to baseline patterns (within a value of 20 mmHg of systolic and diastolic and 20 beats per minute of heart rate relative to their baseline reading).

Each maximal exercise test will be administered by a trained exercise physiologist and exercise technician. The exercise technician should be the staff member who records the required values of each stage and assists with test administration. The exercise physiologist should be the staff that leads the exercise test and provides verbal cues to the participant. The exercise testing will be used to measure changes in fitness levels after 6-months and 12-months. The room should be set at a comfortable temperature (recommended between 60 – 70 degrees Fahrenheit), have necessary fans in place, and have access to water for the participants. The exercise physiologist will also be responsible for examining the ECG read-out and anyone displaying any questionable patterns will have the ECG read by a consulting cardiologist for the team for confirming safety or need for additional follow-up with the participants PCP or cardiologist. Continued eligibility for the study will be dependent upon this consultation and follow-up.

Also at this visit, participants will be fitted with a commercially available physical activity monitoring device (Actigraph Link) around the non-dominant hand wrist that will record objective physical activity data over the duration of approximately one week. The participants will be provided with detailed instructions regarding wearing of the device as well as the option to remove the device if it becomes problematic. Participants will complete a series of questionnaires at this visit.

Once the  $VO_{2max}$  session is complete, participants will be given the NCI diet history questionnaire, via a link and study code that is unique to each participant. Participants will have the option to complete the questionnaire online at their home or via a paper based method to be returned to the eBACH staff.

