#### **1.5.5** TIME POINT 2 (6 months):

At 6-months into the exercise sessions, the participants will complete the assessments that were conducted at baseline. These assessments should be completed within a 1 month window; therefore 2 weeks before their midpoint date or 2 weeks after their midpoint date. The EMA measurement will be completed at month 5 to ensure all other key physiological assessments are completed on time.

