#### 1.5.6 TIME POINT 3 (12 months – post intervention):

At the 12-month session, participants will complete all the assessments that were done at baseline and 6 months. These assessments should be completed within a 1-month window; therefore 2 weeks before their end date or 2 weeks after their end date. It is encouraged to complete session 1 and session 2 within 2 weeks of the intervention completion. If someone is going on vacation after the intervention, then they may be brought in during their last week of intervention for the 12-month assessments. The EMA assessment will begin at Month 11 to ensure all other key physiological assessments are completed on time.

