#### 1.6 **RANDOMIZATION**:

After the completion of the baseline measures and sessions described above the participants will be randomly assigned to one of two groups. These include (a) an exercise condition that will consist of 150 minutes per week of moderate-to-vigorous intensity exercise, or (b) a PA and health information group. We will use a computer randomization protocol that will incorporate a verification that all session visits have been completed and data entered into the database. We will use a minimization algorithm with equal allocation to one of the two groups. The use of the minimization strategy will ensure treatment balance on the two factors of age at study entry (=<42, >42) and gender. Once randomized, an assigned staff member will contact the participant via phone with the group information. On this contact, the staff member will give information such as date, day, time, and location of the subject's first intervention session.

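### The blood-pressure rule for starting the maximal VO2 test is printed backwards: readings above 220/110 are called safe and only those participants may go on

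*Combined protocol and SAP*

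**What the plan says.** Section 1.5.3, Session 1, describes a maximal treadmill VO2 test. It begins with a 5-minute warm-up, after which blood pressure is read and a go/no-go rule applies: "Only participants with safe blood pressure readings (>220/110) will be allowed to continue".

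The same section has three other statements that bear on blood pressure:

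- Before the test, at the start of the session: "Participants will have their blood pressure taken (clinical read) to re-verify eligibility". The limit this serves is in the exclusion criteria (section 1.5.2), which bar a systolic pressure of 160 mmHg or more and/or a diastolic pressure of 100 mmHg or more.
- After the test, a participant may leave once vital signs are back "within a value of 20 mmHg of systolic and diastolic and 20 beats per minute of heart rate relative to their baseline reading".
- On the source of the methods: "These procedures are recommended by the American College of Sports Medicine for graded exercise testing". No numeric limits from that source are printed.

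The test is repeated. At 6 months "the participants will complete the assessments that were conducted at baseline", and at 12 months "participants will complete all the assessments that were done at baseline and 6 months".

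**The concern.** The parenthesis defines which readings count as safe, and it names the high ones. Followed to the letter, the rule sends the participants with the highest pressures to maximal exertion and stops everyone else.

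This is an operative safety threshold, so it should not depend on the reader silently reversing it. Two consequences follow from the wording alone. A test properly run in a participant with normal blood pressure departs from the written protocol. A test run in a participant with a very high reading complies with it.

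The matter is confined to participant safety and protocol accuracy. It does not reach the estimand, the endpoints, the power or the analysis.

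**Working it through.** No sample-size or power figure is involved, so the check sets the rule against the rest of the protocol.

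**1. Apply the rule as printed and with the sign corrected.** The two readings below are illustrative.

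| Post-warm-up reading | As printed (continue only if above 220/110) | Corrected (stop if above 220 systolic or above 110 diastolic) |
|---|---|---|
| 230/115 | continues | stopped |
| 130/80 | stopped | continues |

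Both outcomes reverse.

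**2. Compare with the entry criterion.** An eligible participant has a systolic pressure below 160 and a diastolic pressure below 100. To satisfy the printed rule on both components after 5 minutes of warm-up, that person would need:

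- systolic rise of more than 220 − 160 = 60 mmHg
- diastolic rise of more than 110 − 100 = 10 mmHg

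Starting from 130/80, the rises needed would exceed 220 − 130 = 90 mmHg and 110 − 80 = 30 mmHg. A rule requiring this cannot be intended. Read as an upper limit, 220/110 is coherent: it sits above the resting cut-off of 160/100 and stops people whose pressure climbs too far.

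**3. Look for a correction or a second limit.**

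- The clinic reading precedes the test and serves eligibility. The protocol does not say that the 160/100 limit also governs the follow-up tests.
- The 20 mmHg figure decides when someone may go home.
- Blood pressure is read every two minutes during the test, but no numeric stopping value is printed. The test ends on symptoms or exhaustion.
- The cited professional guidance may hold limits, but they are not reproduced.
- The amendment text at the end of the document does not mention the rule.

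The reversed sentence is therefore the only numeric blood-pressure limit printed for going from warm-up to the maximal test.

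**4. Could the sign be a PDF conversion error?** Inequality signs read correctly elsewhere. Section 1.6 has both directions side by side in "the two factors of age at study entry (=<42, >42) and gender". Less-than signs also survive in the power section (1.4.1), the English-fluency exclusion (1.5.2) and the attrition figure in the amendment text. A misread sign cannot be fully excluded, but nothing points to one.

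**5. Count the occasions.** Baseline + 6 months + 12 months = 3 time points. The documents give no count of affected tests, and none is claimed.

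**The case against.** The strongest reply is that this is a typographical slip that corrects itself. The word *safe* gives the direction, and the parenthesis can be read as loose shorthand for the cut-off that marks an unsafe reading. An exercise physiologist could hardly take 230/115 as the only passing range.

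The trial's own progress supports this. Section 1.5.2 requires that a participant be able to complete the treadmill test, and section 1.6 requires all baseline visits to be verified as complete before randomization. The amendment text reports 57 people randomized. Literal use of the rule would have blocked nearly all of them, so staff evidently used the intended upper limit. That is a strong inference, though not direct proof.

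There are also safeguards that do not depend on the sign: "Each maximal exercise test will be administered by a trained exercise physiologist and exercise technician", ECG is monitored continuously, blood pressure is taken every two minutes, questionable ECG patterns go to a cardiologist, and a defibrillator is in the room.

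Finally, the hypertension exclusion concerns trial eligibility rather than a reading taken after a warm-up, so it supports only the general direction. The documents settle neither what happens at exactly 220 or 110 nor whether one value or both must be exceeded.

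All of this stands, and it limits the weight of the point. It does not make the sentence right. A go/no-go safety rule should be correct as written, and no other sentence in the protocol supplies the correct limit.

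**Conclusion.** The inequality is reversed as printed, and the point is minor. Confidence is high for the wording error; no consequence for any participant is shown or claimed. The practical risk is small, because the intended meaning is plain and the test is closely supervised.

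The conclusion rests on one assumption: that the sign in the source document is the one quoted. The printed page will settle that. Whether 220/110 is a suitable level has not been examined, since the protocol gives no specific source for it; only the direction is at issue.

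**What to change.** Replace the sentence with a stopping rule, for example: *Participants whose post-warm-up reading exceeds 220 mmHg systolic or 110 mmHg diastolic will not continue.*

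The study team should confirm two details that the present text leaves open: that exceeding either value is enough to stop the test, and how a reading exactly at 220 or 110 is handled. The same wording should apply at baseline, 6 months and 12 months.

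The cost is a one-sentence protocol correction, with no effect on analysis, sample size or recruitment.

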#### **Session 2: EMA INFORMATION**

This visit will take approximately three hours and the entire session will occur at Sennott Square in Oakland. The visit entails a clinic blood pressure assessment, and therefore participants will follow the same pre-visit restrictions as visit 1 (no exercise or drinking alcohol after 9:00 pm the night before, no over-the-counter medications 12 hours prior, no food or drink (except water), no smoking, using nicotine, or consuming caffeine 3 hours before the visit). Participants will be notified of these restrictions by a phone call made by a research assistant at least one day prior to the visit. This call and all calls to the participant during the daily monitoring phase will be made from the study cell phone.

Additionally, participants will complete several questionnaires assessing their physical and emotional well-being.

At this visit participants will also receive training on how to use several ambulatory monitoring devices that they will carry with them during the 10-day daily monitoring phase of the study. These devices will measure physical activity and sleep (actigraphy wristband), ambulatory blood pressure (portable blood pressure device, belt, and cuff), and daily psychosocial stressors (Diary of Ambulatory States [DABS] completed on a smart phone). Participants will receive detailed instructions on how to use these monitoring devices, including an option for removal if any of them present a problem. Following the 10-day monitoring period, we will collect the devices, and after we download the data we will clean and sanitize them so that they can be used by other participants in the study. While participants wear the devices they will not be able to view any data.

After the training session, participants will leave the lab practice using the monitoring equipment for the rest of the day and for the morning of the following day. Around late morning, a research assistant will call participants for their 15-minute "Practice phone call," in which they will be given assistance with any problems or questions that may have come up during the practice period.

Following the practice phone call, participants will be instructed to begin the 10-day monitoring phase. This phase consists of four "full" monitoring days (using all devices and completing all interviews) and six "partial" monitoring days (using only the actigraphy device and the electronic diary to complete a morning interview and an evening interview).

On the "full" days, participants will have their blood pressure taken every hour they are awake. Following each blood pressure reading, they will complete a 2-5 minute questionnaire (DABS) about their thoughts and feelings using the

electronic diary. If the participant uses nicotine, they will be trained to activate the electronic diary every time they use a nicotine product. Participants will wear the actigraphy wristwatch while they are awake and asleep. Before participants go to bed, they will be prompted to turn off the blood pressure device and set a wake-up alarm on the electronic diary for the following morning. Once they wake up from this alarm the following day, they will turn back on the ambulatory blood pressure monitor and put it on within 45 minutes. These 45 minutes allow for grooming, showering, and other morning routine activities. On two of the "full" monitoring days, participants will also wear the blood pressure monitor overnight, however they will not need to complete the hourly electronic diary questionnaires overnight.

On the "partial" monitoring days, participants will not wear the blood pressure monitor or complete the hourly electronic diary interviews. The actigraphy wristwatch is worn on both "full" and "partial" monitoring days of the study (including every night of sleep during the monitoring phase).

Several additional phone calls will be scheduled for the first or second day of the monitoring phase in order for a research assistant to answer any of the participants' questions and asses any difficulties they may be having. Similarly, another phone call will be made on the third or fourth day of the monitoring phase in order to confirm that the equipment is still working correctly and to review instructions with the participant.

On two separate non-"full" monitoring days during the daily monitoring period, participants will be instructed by a research assistant to complete the Automated Self-Administered Recall System (ASA24) outside the lab.

#### **Session 3: CARDIOVASCULAR HEALTH**

This visit will take place at Old Engineering Hall, will last (~3 hours), and will be conducted by a trained researcher. It involves returning the EMA equipment to research staff for data retrieval, assessment of pulse wave velocity and endothelial function, and additional questionnaires.

#### EMA Device return:

Participants will arrive to the visit wearing their devices. They will take off their devices and a research assistant will review the data that was collected over the 10-day period. If it is determined that the participant did not complete the expected number of interviews and blood pressure readings, they will be asked to complete extra day(s) of monitoring to provide complete assessments.

Participants will be asked about their compliance with pre-visit instructions (same as Visit 1 plus an additional instruction to wear loose clothing that allows research staff to attach heart-activity measuring devices without disrobing). Similar to the previous visits, these instructions will be given during a phone call made by a research assistant the day prior to the visit. While the research staff is reviewing

the participants' daily monitoring data, participants will complete a number of psychosocial questionnaires.

#### Cardiovascular Assessments:

Following the return of the EMA devices, three separate (non-invasive) protocols will be administered to assess aspects of the participant's cardiovascular health/function:

Autonomic Function and Arterial Stiffness: Self-adhesive sensors will be applied to the participant (on the back of the neck, upper chest, shoulders, ribs, and calf area below the knee) to record their electrocardiogram and monitor changes in thoracic/calf impedance due to blood flow (dual-impedance cardiography). Continuous beat-by-beat BP will also be monitored using cuffs placed around the participant's non-dominant arm and the index/middle fingers of the opposite hand. Recordings will be taken for 5 minutes while the participant is at rest and breathing normally, and also during a paced-breathing protocol (i.e., 11 breaths per minute). From these recordings we will gather key measures of HRV, BRS, and pulse wave velocity (PWV).

Endothelial Health: Venous occlusion plethysmography (VOP) will be used to assess the participants' endothelial function. First, participants are comfortably seated and outfitted with the necessary equipment, including: an occlusion cuff for both their wrist and arm, and a strain gauge wrapped around their forearm. During a standard sequence of cuff inflations/deflations, the participants' forearm blood flow is measured via changes in forearm circumference (as indexed by the gauge). Following "baseline" readings, the arm cuff is inflated to 40 mmHg above systolic pressure for 5 minutes until it is released and "max" readings recommence. This post-occlusion state is referred to as reactive hyperemia and provides a reliable index of endothelium dependent vasodilation. The participant's max flow readings are compared to their baseline readings to derive a percentage increase, with greater values associated with better health.

Pulmonary Function: Participant's lung function will be measured using spirometry. While standing, individuals are instructed to inhale/exhale into a mouthpiece under normal and forced/maximal conditions. From these tests a participant's forced volume capacity and forced expiratory volume can be determined.

#### Blood Draw:

Lastly, a trained phlebotomist under the supervision of [name] (Co-I) will conduct a blood draw for inflammatory and metabolic measures and a hair collection sample to assess hair cortisol levels.

Site specific laboratory safety policies when handling human blood samples will be followed including the use of Biological Safety Cabinets and Personal Protective Equipment/PPE: gloves, lab coat/gown, glasses, and face mask at all times when working with specimens in the lab.

Participants will be asked to abide by the following fasting restrictions prior to the session: nothing to eat or drink (including alcohol and caffeine) except water from 9pm the night before; no exercise for 12 hours prior to the session; no nicotine/smoking 3 hours prior to the session; no cold/allergy or headache medication (aspirin, ibuprofen or other NSAID) for 12 hours prior to the session. A researcher will call the participant the night before the appointment and ask if they have taken antibiotics in the past 2 weeks, or if they have a current infection or cold symptoms (see attached Blood Draw Eligibility Questionnaire). If so, they will be rescheduled. Participants will also be rescheduled if they have had anything to eat or drink except water since 9pm the night before their appointment or report acute illness symptoms.

Blood will be delivered to the Behavioral Immunology Laboratory (605 OEH) of [name] within 30 minutes of the time of the blood draw. Blood will also be delivered to UPMC Central Labs for glycemic and lipid assays.

*Hair strands:*  $\sim 50$  mg; 100-150 strands will also be collected with fine scissors as close as possible to the scalp from the upper part of the back of the head so that it is not noticeable. The samples will be retained by the Behavioral Immunology Lab and tested for cortisol levels.

